Assessments and intervention sessions will occur at the Providence VAMC. The veterans will be informed that their VA medical records will note their enrollment in a research study with a copy of their consent form attached. In addition, their attendance at each AE or HEC session will be noted in their medical records. This will include, if applicable, any safety issues (e.g., suicidal or homicidal statements they made) and how these were addressed in session. The veteran will be informed that none of the other data from this study will be included in their medical records, except for attendance at intervention sessions. All study data, stripped of identifying information, will be locked in a file cabinet as described above. Records will be maintained per Veterans Affairs Record Control Schedule 10-1.

6. Data Safety and Monitoring

Monitoring of safety in the proposed study will be the responsibility of all personnel on the project, with primary responsibility and supervision by [name]. The Institutional Review Board at the Providence VA Medical Center will approve the protocol and the

Statement of Informed Consent for the study and will provide oversight of data and safety issues.

Separate review of the protocol and consent form are made by the safety officer at the VA Medical Center. The study protocol will receive IRB approval prior to soliciting or requesting consent from any participants. Moreover, the study will be reviewed on an annual basis by the IRB committee with regard to recruitment and retention and annual reports will be made by the PI to the IRB chair of the Providence VA Medical Center regarding the progress of the proposed project, including any issues pertinent to recruitment, retention, confidentiality, and safety of human subjects. Any incidents that involve a breach of this plan or serious accident/injury will be reported to the IRB chair at the Providence VA Medical Center. As discussed, potential risks, albeit minimally likely, include distress or discomfort with questions regarding trauma history.

Adverse Event Reporting

In the case of an Adverse Effect (AE) or a Serious Adverse Effect (SAE), a written report of the AE or SAE will be prepared for the Chair of the IRB at the Providence VA Medical Center. Any such AEs or SAEs will be presented to the full IRB committees. SAEs will be reported within 24 hours. Examples of serious adverse effects include death, life-threatening adverse events, suicide attempts, and inpatient hospitalization. The report of such AEs or SAEs will include whether they were expected or unexpected, a rating of severity of the event, a brief narrative summary of the event, a determination of whether a causal relationship existed between the study procedures and the event, whether the informed consent should be changed as a result of the event, and whether all enrolled participants should be notified of the event. The annual progress reports to the IRB require summary information regarding all AEs and SAEs occurring during that year. We have appointed [name] as our medical monitor. [name] is a Providence VA Medical Center physician and researcher who works independently from our research. He will be called upon to review all AEs and SAEs, and to provide input regarding the possible connection to the study protocol.

7. Risks / Benefits Assessment

A. Protection Against Risks

Potential risks include distress associated with discussing traumatic or other disturbing events or emotions, and breach of confidentiality.

Risk: Emotional distress associated with discussing traumatic or other upsetting events or emotions.

Minimization: Study participants will participate in assessments and treatment sessions during which they may identify and discuss difficulties they are having with anger and with their adjustment home from a hazardous deployment. They also may discuss upsetting events that they experienced while deployed. Although the assessments are

unlikely to be more upsetting than standard clinical assessments, discussion of these experiences may make them feel uncomfortable. Should this happen, veterans will be informed that they can refuse to answer any question they wish or stop the interview at any time. Any participant verbalizing or showing signs of distress will be asked to remain in the assessment or treatment setting until their distress is at a manageable and comfortable level. No participant judged to be in danger of hurting him/herself or others will be allowed to leave the study setting unaccompanied. All study personnel who interact with study participants will have been professionally trained to respond to negative emotions if these should occur and to access emergency services if necessary.

Collateral participants will also be informed that they may refuse to answer any question or stop the interview at any time. It is unlikely, but possible, that a collateral participant may show signs of distress. The same procedures will apply to these participants, i.e. if distressed they will remain in the assessment setting until their distress is at a manageable level. [name] will be available by phone or in person to study personnel during assessment and treatment sessions. She will be contacted immediately if there are any concerns about the participant's emotional state, or upon any signs of suicidal or homicidal risk. All participants will be eligible for emergency services including referral to the Veterans Affairs Medical Center interim care during normal business hours or the emergency room after hours and on weekends and holidays, and inpatient hospitalization.

Additionally, therapists will be doctoral level psychologists or masters level social workers, and trained to help veterans reduce and manage feelings of intense anger. Assessments will be conducted by trained staff with prior experience in conducting clinical interviews in psychiatric samples. Veterans will have the opportunity to discuss any uncomfortable feelings with the assessment interviewers and treatment providers. The veteran will also be informed that the therapist and assessment interviewer will always place the veteran's well-being and safety over research considerations. Furthermore the veteran will be informed that should they experience any problems, they should report them to their therapist or to the principal investigator of this study.

Risk: Breach of Confidentiality

Minimization: All employees who handle data will be trained in confidentiality policies and procedures. All data and medical information obtained about the veteran, as an individual, will be considered privileged and held in confidence; the veteran will not be identified in any presentation of the results. Assessments and treatment sessions will occur at the Providence VAMC. Veterans will be informed that their VA medical records will note their enrollment in a research study with a copy of their consent form attached. In addition, their attendance at each therapy session will be noted in their medical records. This will include, if applicable, any safety issues (e.g., suicidal or homicidal statements they made) and how these were addressed in treatment. The veteran will be informed that none of the other data from this study will be included in their medical records, except for attendance at treatment sessions. All study data, stripped of identifying information, will be locked in a file cabinet. Study files will be maintained in

accordance with the Department of Veterans Affairs Record Control Schedule 10-1.

All of the study data will be coded without the use of the veteran's name and social security number and will be done in accordance with the law. Research information about the veteran will remain in [name] (PI) locked private research files and will be available only to staff connected with this study or individuals involved in human subjects protection. It will not be given to other medical care personnel at the veteran's VA or the Department of Veterans Benefits without an additional written consent from the veteran. Any reports or publications of this study will not include information that could be used to identify the veteran.

Measures will be identified with a study ID number not based on a personal identifier. A cross-index of names and ID numbers will be stored in a separate locked location from all data. Transfer of data will include only de-identified data, and will use encryption for any electronic transfer. Additional precautions include: (1) Data sheets will be stored in locked offices of [name] (PI), building 32 of the PVAMC, (2) data will be entered in coded form, (3) data will be stored in computer files protected from unauthorized access by passwords, (4) information that might potentially allow an individual participant to be identified will not be allowed in any publications or reports sent to individuals outside the study, and (5) all employees who are to handle data will be trained in confidentiality policies and procedures.

Digital recordings will be made of all treatment and assessment sessions. These recordings will be reviewed by study personnel who are providing ongoing supervision to study therapists and interviewers, and by individuals conducting reviews of how well we followed study procedures (adherence ratings). These recordings will be coded without the use of the veteran's name or social security number, or any other identifying information.

Digital recordings may also be downloaded into a file transfer program (FTP) which is password protected. Research staff will be the only people to have access to the FTP. Study files will be maintained in accordance with the Department of Veterans Affairs Record Control Schedule 10-1.

B. Potential Benefits of the Proposed Research to the Subjects and Others

Poorly controlled anger is a common problem with often devastating effects in veterans who have been exposed to trauma while they served in a warzone. Additionally, individuals who have experienced trauma may continue to respond with excessive anger and aggression in situations that they perceive as threatening (even in the absence of life-threat) resulting in destruction of property, threats of physical violence and/or physical fights. Although this response may have been adaptive during trauma, it is maladaptive when individuals cannot regulate the intensity and expression of anger as appropriate with current socio-environmental conditions. There is empirical support for the use of Cognitive Behavioral Therapy (CBT) similar to what we propose in the treatment of other populations with anger, and preliminary support for positive effects in veteran

samples.

Through participation in this study, the veteran receives a comprehensive psychological assessment and treatment at no cost. Additionally, potential effects of the interventions could possibly lead to an improvement in the veterans' ability to manage their anger and adjustment to being home following deployment. Furthermore, it is hoped that information gained from this study will improve treatment for veterans who have served in hazardous deployments, even if the veteran themselves do not experience any improvement during their participation in the study. Given the published reports and our own experience, the potential benefits outweigh the risks.

C. Importance of the Knowledge to be Gained

Problems with anger are common in veterans who have been deployed to a warzone, and can lead to devastating consequences in terms of family, social, and occupational functioning. Although promising findings for cognitive behavioral treatments have been reported, to date there is not a single adequately powered randomized trial designed to test the efficacy of an anger treatment compared to an active control condition in veterans. The goal of the proposed research is to determine if the Cognitive Behavioral Intervention to be tested can provide an effective treatment for anger problems in OEF/OIF veterans, and reduce the toll that these problems take on social and occupational functioning and quality of life. The potential of the research to ultimately benefit veterans with anger problems, and the provision of comprehensive assessment and treatment compares favorably when weighted against the potential risks of discomfort or distress, which are expected to be mild.

PROTOCOL APPENDIX - ISO

All VA sensitive information will be stored on the secure VA server located at:
\\vhaproapp12\\Research_Protocols\\[name]\\Anger-R

All data is collected using a study code that does not identify the patient. The cross-link matching the patient with the code is saved in a password-protected file, separate from the rest of the data files, on the same secure VA server that only the PI and research staff have access to. Paper versions of the assessment will be stored in locked filing cabinets in locked offices of [name] (PI), in building 32 of the PVAMC. Additionally, no VA sensitive data will be transmitted outside the VA. Only VA non-sensitive data will be transmitted electronically via internet for discussion during study meetings. Data collected from this study will be used for research purposes. No patient identifiable information will be released or published without written permission unless required to do so by law. Records will be maintained in accordance with the Department of Veterans Affairs Record Control Schedule 10-1.

In the event that theft, loss of other unauthorized access of sensitive data or storage devices and non-compliance with security controls occur, study staff has been instructed to follow the Providence VA Medical Center's standard operating procedure on incidence reporting.

Transcription records will be maintained according to RSC 10-1. All digital recordings will be uploaded to the server for storage. Once the records are copied and verified from the recording device, the device will be turned into the ISO for final disposition.

Original data files on portable storage media, i.e., CDs, USB Flash Drives, etc, will be uploaded to the server for storage. Once the files are copied and verified from the device/media, the device/media will be turned into the ISO for final disposition.

Original data collected on non-digital storage media, such as audio tapes, will be maintained in accordance with VA RCS-10-01.

We will use REDCap electronic data capture tools hosted at the Department of Veterans Affairs. REDCap (Research Electronic Data Capture) is a secure, web-based application designed to support data capture for research studies. Through REDCap, participants are able to respond to survey items electronically and additionally research study staff can manually enter responses. All study software and licensing, such as SPSS IBM (which will be used for data analyses) will be managed by PVAMC IT and IRM.

References

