(1) To investigate the efficacy of CBI on primary measures of anger treatment outcome. We hypothesize that:

- a) Compared to SI, CBI will be associated with significantly larger reductions in anger and aggressive behaviors at post-treatment and at 3 and 6 month follow-ups.

(2) To investigate the efficacy of CBI on secondary measures of anger treatment outcome. We hypothesize that:

- a) Compared to SI, CBI will be associated with significantly more improvement in social functioning, occupational functioning, quality of life, and PTSD symptoms at post-treatment and at 3 and 6 month follow-ups.

(3) To examine mechanisms of action of CBI. We hypothesize that:

- a) Change in arousal, cognitive, and behavioral domains of anger will mediate outcome for anger and functioning in the CBI condition.

(4) To examine the effectiveness of CBI for those with and without PTSD. We hypothesize that:

- a) CBI will be superior to SI on primary and secondary outcome measures (aims 1 and 2) for those with and without PTSD.

2. Background, Significance, and Rationale

Anger Problems in Military Personnel and Veterans: Poorly controlled anger is a common

problem with often devastating effects in veterans who have served in a warzone. As early as World War II, anger and aggression were identified as common responses to combat stress ^{1, 2}, and the association between combat experience and symptoms of anger and hostility has repeatedly been demonstrated in empirical research ^{3, 4, 5}. Findings from the National Vietnam Veterans Readjustment Survey⁴ showed that Vietnam veterans exposed to high levels of war stress expressed higher levels of hostility and committed more violent acts compared to Vietnam era (non theatre) veterans, civilians, and theatre veterans exposed to lower levels of war stress. Excessive anger and difficulty managing anger were also shown to increase risk for divorce, domestic violence, job loss and instability, and other serious impairments in family, social, and occupational functioning ⁴.

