All major variables will be screened for inconsistent or abnormal values, and continuous measures will be assessed for skewness and outliers. Transformations to improve normality may be applied to continuous variables. Missing data rates and patterns will be assessed; in particular, missing data rates by treatment group will be studied. Although randomization tends to produce well-balanced treatment samples⁵⁹ analyses will be carried out to determine any baseline differences between the treatment groups on demographic or other prognostic variables, using chi square analyses for discrete variables and ANOVA for continuous ones. If significant treatment group differences are found on potentially important baseline variables, these variables will be covaried in outcome analyses. Data from all randomized study participants will be used to compare the outcome of the two interventions on an intent-to-treat basis. Hypothesis tests will be two-tailed.

Participants will be counted in the intervention group to which they were randomized, regardless of the number of sessions they completed. We will make every attempt to complete a post-treatment and 3 and 6 month follow-up assessments on any participants who do not complete treatment. We will also conduct supplementary analyses including only those cases completing the full 12 sessions.

Aim 1: Investigate the effectiveness of CBI on primary measures of outcome

Hypothesis: Compared to SI, CBI will be associated with significantly larger reductions in anger and aggressive behaviors at post-treatment and at 3 and 6 month follow-ups.

Aim 2: Investigate the effectiveness of CBI on secondary measures of outcome

Hypothesis: Compared to SI, CBI will be associated with significantly more improvement in social functioning, occupational functioning, quality of life, and PTSD symptoms at post-treatment and at 3 and 6 month follow-ups.

For aims 1 and 2, we will use hierarchical linear modeling (HLM) for repeated measures to test for differences due to treatment condition, covarying for the baseline score of the dependent variable⁶⁵. The primary significance test will be the treatment group main

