effect over time, though there will also be a test for the time by treatment interaction. Significant time by treatment interactions will be followed up by post hoc tests at specific assessment points by calculating simple intercepts, simple slopes, and regions of significance. Relevant covariates will be included to adjust for any imbalances across treatment conditions.

Missing data will be dealt with as follows. HLM analyses can include cases with some time points missing. In the primary analysis, we will include all cases with at least 3 of the 5 outcome time points (4 & 8 weeks, posttreatment, and 3 & 6 months) non-missing. Then, we will conduct a sensitivity analysis including all randomized participants, in which any missing outcome values will be filled in with baseline scores, which is an extreme assumption. Consistency of results from the two approaches will bolster the credibility of the primary analysis.

The primary dependent variables for aim 1 are the STAXI-2 Anger Expression Index, and the OAS-M Aggression Scale score. Outcome on these measures is assessed at 4 and 8-week points during treatment, at post-treatment, and at 3 and 6 months follow-up assessments. DVs for aim 2 include two LIFE scales (global social and work functioning), the Outcomes Questionnaire total score, the WHOQOL-BREF total score, and the CAPS total score. Outcome on these measures is assessed at post-treatment and 3 and 6-month follow-up assessments.

For aims 1 and 2 the alpha will be set at .025 to account for multiple dependent variables.

Supplementary post-treatment outcome analyses will be conducted using collateral measures (including the STAXI-II, Anger Control Scale and Modified Overt Aggression Interview). We will calculate Pearson correlations of participant and collateral scales as an indication of agreement. If outcome analyses based on collateral measures are consistent with analyses of participant measures, this would bolster the validity of the participant outcome findings. Divergent findings could be due to multiple factors that could influence the validity of the participant and the collateral reports. In this case we will conduct analyses using integrated collateral and participant scores, calculated by averaging the participant and collateral responses to each item.

Aim 3: (Exploratory) Examine hypothesized mechanisms of action of CBI

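### Aim 1 names post-treatment, 3 and 6 months, but arm contrasts at those visits are planned only after a significant time-by-treatment interaction, so a positive trial may report none of them

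*Combined protocol and SAP*

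**What the plan says.** The Aim 1 hypothesis (section 1, repeated in G.2) is that CBI gives "significantly larger reductions in anger and aggressive behaviors at post-treatment and at 3 and 6 month follow-ups".

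G.2 specifies a hierarchical linear model for repeated measures, "covarying for the baseline score of the dependent variable". The decision rule is one sentence split across a page: "The primary significance test will be the treatment group main", continuing "effect over time, though there will also be a test for the time by treatment interaction". For the two primary measures, the STAXI-2 Anger Expression Index and OAS-M Aggression, "Outcome on these measures is assessed at 4 and 8-week points during treatment" as well as at post-treatment, 3 months and 6 months. That makes five outcome points, and the hypothesis names three of them.

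On individual visits, G.2 says: "Significant time by treatment interactions will be followed up by post hoc tests at specific assessment points", to be done "by calculating simple intercepts, simple slopes, and regions of significance". It does not say how time is coded or how the five points are weighted in the main effect.

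**The concern.** The hypothesis concerns benefit at the end of treatment and its durability afterwards. The primary test asks whether the arms differ on a summary over five points that includes weeks 4 and 8. The only planned route from that summary to a named visit runs through a significant interaction. A non-significant interaction does not show that the effect is the same at every visit, and in a trial of this size the test has little power against a moderate fade. The trial could follow its plan exactly, be declared positive, and report no CBI minus SI contrast at post-treatment, 3 months or 6 months.

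The point is specific to Aim 1, because the Aim 2 outcomes are measured only at the three hypothesised visits.

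**Working it through.** **Is there another route to the visit contrasts?**
- Collateral reports: "Supplementary post-treatment outcome analyses will be conducted using collateral measures". These come from another informant, are optional for participants and cover post-treatment only. Averaged participant–collateral scores are analysed only if the two sources diverge.
- Aim 3 uses 3- and 6-month outcomes, but in exploratory mediation tests.
- Aim 4 gives effect sizes by PTSD status with no visit stated.

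None is an unconditional participant contrast on a primary measure at a named visit. The gap follows from the text alone; the arithmetic below only shows when it matters.

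**Inputs from the protocol.** N = 120, 80% follow-up, effect .60, two-sided alpha .025 per measure, stated power 90% (G.3); outcome points (G.2); post-treatment at week 12 (D.7).

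**Assumptions.** 1:1 allocation, so .80 × 60 = 48 per arm; compound symmetry with within-person correlation ρ = .62 (range .5 to .7), shared by baseline; effects d in unadjusted SDs; equal visit weights; 3 and 6 months placed at weeks 25 and 38. The interaction is tested at .05, as a 4-df categorical test or a 1-df linear test, because time coding is unstated.

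**The plan's 90%.** The variance of a five-visit mean is (1 + 4ρ)/5 = .696 at ρ = .62. With 48/2 = 24, the noncentrality is .60 × √24/√.696 = 3.523, and power is Φ(3.523 − 2.241) = .900. The figure is attainable, but the plan does not state its ρ. It is not disputed here.

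**Modest fade: d = .60, .60, .60, .48, .36 (mean .528).**
- Primary test, unadjusted: .528 × √24/√.696 = 3.10, power .805.
- Primary test, baseline-adjusted: variance .696 − .62² = .3116; .528 × √24/√.3116 = 4.63, power .992.
- Interaction, 4 df: Σ(d − .528)² = .04608; × 24/(1 − .62) = 2.91; F(4, 376) power .235.
- Interaction, linear: with weeks centred at 17.4, Σtd = −5.856 and Σt² = 779.2; 5.856²/779.2 × 24/.38 = 2.78; F(1, 376) power .383.

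Under compound symmetry the five-visit mean and the interaction contrasts are independent, so the probabilities multiply.

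| Positive primary, no significant interaction | 4 df | Linear |
|---|---|---|
| Adjusted, ρ = .62 | .992 × .765 = .759 | .992 × .617 = .611 |
| Adjusted, ρ = .5 | .802 | .683 |
| Adjusted, ρ = .7 | .705 | .533 |
| Unadjusted, ρ = .62 | .805 × .765 = .616 | .805 × .617 = .496 |
| Adjusted, ρ = .62, interaction tested at .025 | .837 | .713 |

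**The 6-month contrast in that scenario.** Adjusted SE = √((1 − .62²)/24) = .160 SD, and the 97.5% interval half-width is 2.241 × .160 = .359 SD. Power for d = .36 at .025 is .503 (.419 at ρ = .5, .590 at ρ = .7). In 20,000 simulated trials with estimated variances, .329 (4 df) or .219 (linear) had a positive primary test, no significant interaction, and an unreported 6-month contrast that would have missed .025. The range over ρ = .5 to .7 is .427 to .230 and .321 to .136.

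**Fade to zero: d = .60, .60, .60, .30, 0.** Adjusted primary power is .926 and interaction power .943 or .986. Positive and unflagged: .926 × .057 = .053, or .926 × .014 = .013. At ρ = .5 these rise to about 13% and 4%.

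**Constant d = .60.** Adjusted primary power is .999 and the interaction is significant 5% of the time, so .999 × .95 = .949 of trials are positive with no visit contrast.

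**The case against.** The strongest reply is that little harm follows.

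- **The 76% and 61% do not measure error.** They are close to one minus the power of the interaction test and are largest (95%) for a constant effect, where the main effect is correct at every visit. This stands: they show how often the contrasts would go unreported, not how often a conclusion would be wrong.
- **CBI is truly better at every named visit in the modest fade.** The 33% and 22% are therefore low-power misses at 6 months, and what is hidden is the size there (.36 against a mean of .528). This also stands. When benefit vanishes, the interaction usually flags it.
- **The settings are assumed.** The value .62 is simply the one that reproduces 90% without baseline adjustment. The only related figure in the documents, OAS-M test–retest of .46 to .54, would not shrink the result, since lower ρ raises it. The mention of simple slopes suggests continuous time, which favours the smaller linear figures. Against that, applying the plan's .025 alpha to the interaction raises both.
- **Gating visit tests behind an interaction is a conventional guard against multiplicity, and the plan does not forbid reporting visit estimates.** True, but it does not commit to them either, and contrasts chosen after the results are seen carry less weight. Intervals that interpret an unchanged primary test do not alter its error rate.

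**Conclusion.** The concern holds. The plan prespecifies no unconditional CBI minus SI contrast on either Aim 1 primary measure at any visit its hypothesis names, and this needs no numerical assumption. How often it matters does depend on assumptions. With a modest fade, about 76% (4 df) or 61% (linear) of trials would be positive without a visit contrast; with a fade to zero, about 5% or 1%; with a constant effect, only the reporting is incomplete. These rest on 48 per arm, compound symmetry, ρ = .62, baseline adjustment and an interaction alpha of .05. The primary test, its alpha and the stated power are not called into question. The change should be made because the durability claim is the trial's own and the remedy is almost free.

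**What to change.** Keep the five-visit main effect as the primary test. Add to G.2:

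1. For both Aim 1 primary measures, report the model-based, baseline-adjusted CBI minus SI contrast with a confidence interval at post-treatment, 3 months and 6 months, whatever the interaction test shows.
2. State the confidence level (97.5% would match the .025 alpha per measure), and state that these contrasts interpret the primary result and are not further confirmatory tests. If any is to be tested formally, add a multiplicity rule.
3. State how time is coded and how visits are weighted in the main effect. If time is continuous, take the three contrasts from a model with visit as categorical, so that they are not forced onto a line.

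Making a three-visit average the primary test is optional and is not requested here.

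The cost is plan wording and six contrasts (two measures × three visits) from assessments already scheduled. The primary test and its alpha do not change, so there is no loss of power. This version is dated 11/28/18 and the study was to run until 07/31/2018, so the addition should be dated, and labelled as added afterwards if arm comparisons have already been seen.
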